The primary aim of this study is to assess the effectiveness of rural pediatric obesity treatment delivered virtually to family homes (iAmHealthy) compared to an active attention control group (control). This is a cluster randomized design, with schools being assigned to condition (iAmHealthy or control) and the 8 parent/child pairs at each school being assigned to the same condition. Having children and families from the same school participate in the same mHealth group allows us to target the unique environmental characteristics that are both barriers to and facilitators of success in iAmHealthy.

II. Research Plan and Design

A. Design and Intervention.

The intervention is a cluster randomized design as groups will be randomized by school. Schools will be contacted via a flyer sent to all 550 rural elementary schools in the state of Kansas. Schools will contact researchers via a toll-free number and given detailed instructions on how to complete the required human subjects training and earn Institutional Review Board approval. Recruited schools will be stratified by two key variables (school size, percent free/reduced lunch) and then assigned to one of the intervention groups, such that all children/families who sign up at each elementary school will be assigned by school as a single group to either iAmHealthy or control (i.e., randomization occurs at the school level, not at the individual level). Any subsequent schools will be waitlisted for participation the next year.

Once 6 schools are randomized, they will be sent research grade scales and stadiometers and trained by research staff in all measurement and intervention procedures. At this time school representativeness will be analyzed each year, and if schools are not representative on either of the key metrics, schools recruited the following year will be oversampled in order that schools reach a representative sample by the end of the 5-year study.

The iAmHealthy family-based intervention provides behavioral, nutrition, and physical activity topics (see Table 4 and Appendix A). The intervention has an 8-week intensive weekly intervention phase followed by a 6-month period of

Table 4. iAmHealthy Standard Int	Rurally Tailored Topics	
Goal Setting & Sticker Charts	Reading Food Labels	Decreased focus on fast food
Stop Light Diet Parent Health Behavior Changes	Energy Balance Use of Privileges	Increased focus on eating at social gatherings

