 of children who express interest in the program divided by the total number of children eligible. Percent enrolled
 will be calculated as the total number of children who complete enrollment procedures divided by the total number
 of children who expressed interest.
- 2. *Adoption.* Adoption will be measured by calculating the representativeness of the participating schools. Specifically, participating schools will be measured on their student body size and their percent free/reduced lunch and will be compared as a group to the overall data that is available for all elementary schools in the state of Kansas on these key variables to assess for the representativeness of participating schools.
- 3. Attendance and Participation. Percent attendance will be calculated for each parent/child pair as the percent of sessions attended divided by the total number of sessions offered. Participation will be assessed for both groups by asking the parents and children about additional health related information they sought to supplement the content of the program, such as health websites, apps, books, programs, etc. For both groups participation will also include the amount of homework that was completed from the sessions (as a percent) self-reported as part of the Post Questionnaire at the 8-month time point.
- 4. *Cost.* Cost will be analyzed in terms of cost effectiveness, defined as cost per unit change in BMIz, by our experienced health economist ([name]). The cost perspective will be societal, meaning that both provider and client costs will be measured.⁵⁰
- 5. *Group Process Factors.* In order to assess factors related to the group process for the iAmHealthy intervention, as well as to assess for engagement in the group sessions, we will use the Living in Familial Environments Coding System. ^{55,56} Per proper procedures, only initial sessions will be coded for the 15 content codes (facilitative, solicitous, self-positive, problem statement, proposed solution, complaint, oppositional, command unaccountable, self-complaint) which fall into 3 categories (positive, negative, neutral). This coding will be completed for each parent and child separately and allow for a calculation of child engagement and parent engagement uniquely.
- 6. *Pedometer Steps.* Both parents and children in the intervention group will be asked to track their steps throughout the study. We will provide Garmin Vivofit devices to parents and children, or the family may choose to use a device

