Some outcomes will be analyzed using the multilevel model described above with a baseline covariate. These outcomes include Efficacy outcomes for parent and child reports of HRQOL, parent distress, child depression, and child peer victimization. A second set of outcomes involve tests of treatment condition differences where a baseline covariate is not available. These outcomes will be analyzed similarly with a multilevel model, however there will not be a level-1 covariate for the outcome at baseline. Outcomes to be analyzed in this manner include: parent and child satisfaction within Efficacy as well as attendance, participation, and cost from Implementation. The stigma outcome within Efficacy will be analyzed by comparing the proportions reporting child stigmatization between treatment conditions. This will be done for both child and parent report. A third set of outcomes will be examined descriptively. These outcomes include participation from Reach as well as descriptions of the barriers obtained in the qualitative analysis, school-level demographics from Adoption, engagement from Implementation, the number of schools retaining intervention components and summaries of factors related to maintenance from Maintenance. Participant demographics, reported food insecurities, and technological feasibility will also be examined descriptively.

Missing Data. While attrition and incomplete data may be unavoidable, the deleterious effects missing data may have on our results can be mitigated through a combination of careful data collection and thoughtful analysis. Full information maximum likelihood estimation which uses all available data to build a multidimensional likelihood function for each highest-level unit (schools) will be used for the multilevel models. For variables brought into the likelihood function, any missing cases are assumed missing at random, which means random only after conditioning on model predictors and the observed outcomes. Reasons for student departure (e.g., dropout versus changing schools) can be tracked and included as model predictors to help reduce the bias that might otherwise be created.

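### Adoption is measured on the same two school variables that the yearly oversampling rule corrects, so when that rule acts the final comparison can understate uneven uptake by schools

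*Combined protocol and SAP*

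**What the plan says.** Section II.A sends a flyer to all 550 rural elementary schools in Kansas. Interested schools identify themselves: "Schools will contact researchers via a toll-free number". The section names two key variables, school size and percent free/reduced lunch, as stratification factors. It then requires representativeness to be analysed each year, with this consequence: "if schools are not representative on either of the key metrics, schools recruited the following year will be oversampled". The stated purpose is a representative set of schools by the end of the five-year study.

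Section II.D, Other Variables Assessed, item 2, defines the outcome: "Adoption will be measured by calculating the representativeness of the participating schools". On content, "participating schools will be measured on their student body size and their percent free/reduced lunch", and they are to be "compared as a group to the overall data that is available for all elementary schools in the state of Kansas". No other variable is named. Table 6 lists only the representativeness of participating schools under Adoption, and section II.E places "school-level demographics from Adoption" among the outcomes examined descriptively.

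Nowhere does the plan call for a school-level uptake rate, a comparison of responding with non-responding schools, or separate reporting of schools recruited before and after oversampling.

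**The concern.** A comparison made on the quantities that recruitment is told to correct is partly a record of the correction. If schools of one kind come forward less often, the yearly check may detect it and later recruitment is steered to compensate. The final set then resembles the population more closely than the schools' own response did. A reader who takes the Adoption result as evidence of which schools take up the programme could conclude that uptake was even when it was not. The rule acts when imbalance is seen, which is when an account of uptake is most needed. This holds whichever reference population is used.

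At child level the plan does better. Its participation measure divides children expressing interest by children eligible, and percent enrolled divides those enrolled by those interested. Schools have no equivalent, although the number approached is known.

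**Working it through.** **Overlap of variables.** Recruitment rule (II.A): school size and percent free/reduced lunch. Adoption (II.D, item 2): student body size and percent free/reduced lunch. The two lists are the same.

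**Figures in the plan.** There is no stated Adoption figure to reproduce. The sample size in II.B is consistent: 8 pairs × 18 schools = 144. II.A speaks of 6 schools being randomised. Reading this as 6 per year (an assumption) gives 18 / 6 = 3 batches, so 12 / 18 = 67% of schools enter after the first yearly check. The ratio 18 / 550 = 3.3% is fixed by the design and is not an uptake rate.

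**What full correction would need.** Let m1 be the mean of the first 6 schools and m2 the mean of the other 12, as deviations from the population in SD units. The final mean is (6·m1 + 12·m2) / 18, which is zero when m2 = −m1 / 2. First-batch deviations of −0.4, −0.8 and −1.2 SD are cancelled by later means of +0.2, +0.4 and +0.6 SD.

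**Illustration with a conditional rule.** Assumptions:
- Half of schools are high free/reduced lunch.
- High-lunch schools take up at a ratio r relative to the others, so their share among volunteers is r / (1 + r).
- The rule fires when the cumulative share is at least 1/6 away from 50%.
- When it fires, the next 6 schools are chosen to bring the cumulative share as near 50% as possible.

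Results of 40,000 simulated trials per setting:

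| Uptake ratio r | Expected final share, no rule | With rule | Chance final share is 40–60%, no rule | With rule |
|---|---|---|---|---|
| 1.0 | 50% | 50% | 52% | 78% |
| 0.67 | 40% | 47% | 38% | 73% |
| 0.5 | 33% | 45% | 21% | 64% |
| 0.33 | 25% | 42% | 5% | 49% |

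Hand check at r = 0.5: the volunteer share is 0.5 / 1.5 = 1/3. The rule fires after the first batch unless exactly 3 of 6 are high-lunch, which has probability 20 × (1/3)³ × (2/3)³ = 160/729 = 22%. It therefore fires 78% of the time and brings the total to 6 of 12. The third batch adds 6 × 1/3 = 2 on average, giving 8/18 = 44%, in line with the simulated 45%. Without the rule, 18 × 1/3 = 6, and 6/18 = 33%.

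**Sensitivity to the trigger.** The trigger above is sensitive. Suppose instead that failure meant an exact two-sided binomial test at 5% against 50% (also an assumption). In the first batch, 2 of 6 gives p = 44/64 = 0.69, 1 of 6 gives 14/64 = 0.22, and 0 of 6 gives 2/64 = 0.03. Only 0 or 6 of 6 would fire, with probability (2/3)⁶ + (1/3)⁶ = 65/729 = 9% at a one-third share. So at r = 0.5 the expected final share can lie anywhere from 33% (the rule never acts) to 50% (full correction, needing on average 9 − 2 = 7 of the later 12 schools to be high-lunch).

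**The case against.** The strongest reply is that the plan does what it says. Adoption is defined as the representativeness of the schools that took part, and the final comparison will describe those schools correctly. Nowhere is it said to measure voluntary uptake, so it would be too strong to say that the measure fails its stated purpose. Oversampling also serves generalisability and should stay. All of this stands. What remains is that the result, reported as Adoption, invites an inference about uptake that it cannot carry once the rule has acted.

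A reader might also infer that the result is predetermined, that only the first six schools escape steering, or that any gap will be removed. The documents support none of these. Oversampling is conditional, so if the first check passes, the next year's schools are unsteered too. Six schools a year is an interpretation. A representative final set is an aim and not a guarantee, and waitlisting (surplus schools, and schools unable to recruit 8 pairs) may limit how freely schools can be chosen. In the illustration the skew often remains visible: at r = 0.5 the final share still falls outside 40–60% in 36% of trials.

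The yearly analysis will itself produce the figures needed, although separate reporting of them is not planned. A telephone enquiry is only early interest, since training, ethics approval and recruiting 8 pairs come later. Hence agreeing schools should be counted as well as responding ones.

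**Conclusion.** The concern holds in a limited form. The overlap of variables is plain in the text, and when uptake is uneven and the rule acts, the final comparison is pulled towards the population and can understate the unevenness. The direction is clear but the size is unknown, because the trigger and the method of oversampling are not given. The movement from 33% to about 45% is an illustration that rests on the assumed population share, uptake ratio, batch size and correction rule.

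Adoption is descriptive, so no primary outcome, test or error rate is affected. This is a matter of labelling and reporting that should be put right because the main part costs almost nothing.

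**What to change.** In section II.D, item 2:

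1. Label the comparison of the final 18 schools as representativeness of the trial sample after any oversampling, and state that it is not evidence of which schools take up the programme.
2. Report the yearly representativeness results that II.A already requires, showing schools recruited before any oversampling separately from those recruited after it.
3. Report the number of responding schools and the number of agreeing schools, each over the 550 approached.
4. Where contact records and school-level data exist, compare responders with non-responders on school size and percent free/reduced lunch.

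Items 1 and 2 need only wording and a table. Item 3 needs counts of calls and agreements. Item 4 depends on records that may be incomplete: the plan does not mention a call log, years in which calls were not logged cannot be rebuilt, and the statewide data it refers to may be available only in aggregate. The price is a little more reporting and possibly a less favourable Adoption statement.

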	Weeks 1-8	Weeks 9-12	Weeks 13-16	Weeks 17-20	Weeks 21-24	Weeks 25-28	Weeks 29-32			
iAmHealthy Intervention	8 weekly sessions	1 session	1 session	1 session	1 session	1 session	1 session			
	11 hours of homework help via remote technology									

in the area of pediatric obesity treatment, children who receive at least 25 contact hours over a 6-8 month period are significantly more likely to be successful than children who receive fewer hours.²²

B. Sample Criteria

- 1. Sample Size:
 - a. About 144 parent/child pairs (8 or more parent/child pairs at 18 schools). Approximately 175 parent/child pairs will be consented to have 144 children go on to enrollment.
- 1. Inclusion/Exclusion Criteria:
 - a. Inclusion Criteria:
 - i. Family lives in a rural area (city and/or county population <20,000)
 - ii. Child BMI >85th and <99th percentile
 - iii. Child in 2nd thru 4th grade
 - iv. Both child and parent speak English
 - v. Family is available at times intervention is offered
 - b. Exclusion Criteria
 - i. Child has physical limitation or receives and injury which significantly limits physical activity
 - ii. Child has significant medical issue known to the school (i.e. cancer)
 - iii. Child and/or parents have a significant developmental delay or cognitive impairment that is known to the school

- iv. Child has a sibling already enrolled in the program
- v. Family moves to a non-participating school

C. Enrollment, Consent, and Procedures.

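### Adoption benchmarks the participating schools against all Kansas elementary schools, although only the 550 rural ones are approached; a good rural sample can then be described as unrepresentative, and the yearly oversampling may inherit the same benchmark

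*Combined protocol and SAP*

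**What the plan says.** Four places in the combined protocol and SAP bear on this.

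- **Section II.A, Design and Intervention (frame).** "Schools will be contacted via a flyer sent to all 550 rural elementary schools in the state of Kansas". No other schools are approached.
- **Section II.A (yearly rule).** School size and percent free/reduced lunch are the two key variables used to stratify schools before assignment. After 6 schools are randomised, the plan says: "At this time school representativeness will be analyzed each year". It continues: "if schools are not representative on either of the key metrics, schools recruited the following year will be oversampled". The stated purpose is a representative sample by the end of the 5-year study. This section names no reference population and no threshold.
- **Section II.D, Other Variables Assessed, item 2 (Adoption).** Here "participating schools will be measured on their student body size and their percent free/reduced lunch", and they "will be compared as a group to the overall data that is available for all elementary schools in the state of Kansas". This is the only place that says what representativeness is measured against, and it carries no rural restriction.
- **Section II.E, Statistical analyses.** School-level demographics under Adoption are examined descriptively. No test or cut-off is given.

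Section II.B also restricts enrolment to families in rural areas (city and/or county population under 20,000) and plans 18 schools with 8 or more pairs each.

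**The concern.** Representativeness has meaning only relative to a target population. The target here is rural: the aim, the mailing list and the family eligibility rule all say so. The Adoption benchmark is every elementary school in the state, which brings in schools that were never approached and could not contribute eligible cohorts in the intended way. If rural schools differ from the state on size or on free/reduced lunch, the comparison mixes two things: how well the participating schools reflect rural Kansas, and how far rural Kansas lies from the state. Only the first is the Adoption question.

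Two things are at stake. The first is the Adoption result itself, a named outcome in the measures timeline (Table 6). The second is recruitment. The oversampling rule in section II.A uses the same two metrics and the same term. If it also takes its benchmark from the Adoption item, later cohorts would be chosen to close a gap that is a feature of the target population.

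**Working it through.** **Step 1: the populations side by side.**

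| Element | Population | Where |
|---|---|---|
| Schools approached | 550 rural Kansas elementary schools | II.A |
| Families eligible | Rural | II.B |
| Adoption benchmark | All Kansas elementary schools | II.D, item 2 |
| Oversampling benchmark | Not named; same two metrics as Adoption | II.A |

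The first and third rows differ on the face of the text. That the fourth row follows the third is an inference: the document offers no other definition of representativeness.

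**Step 2: the plan's own figures.** The plan gives no figure for representativeness, so there is none to reproduce. The related sample figure does reproduce: 18 schools × 8 pairs = 144 pairs. With 6 schools per round, 18 / 6 = 3 rounds. Recruitment can then be adjusted after 6 and after 12 schools. At 18 no planned cohort remains, so a comparison there bears only on the final Adoption description.

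**Step 3: an illustration of size.** The documents give no distribution of either metric, for rural schools or for the state, and set no test. The following are therefore assumptions: a true rural-minus-state difference of d standard deviations on one metric; a simple random sample of n rural schools; a two-sided 5% one-sample t-test against the all-Kansas mean; and cumulative checks at 6, 12 and 18 schools.

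The chance of a flag is P(|T| > t(0.975, n−1)), where T is noncentral t with n−1 degrees of freedom and noncentrality d√n. The critical values are 2.571 (n = 6), 2.201 (n = 12) and 2.110 (n = 18). For example, n = 6 and d = 0.5 give noncentrality 0.5 × √6 = 1.225 and a flag probability of 17%.

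| Assumed d (SD) | 6 schools | 12 schools | 18 schools (description only) |
|---|---|---|---|
| 0 | 5% | 5% | 5% |
| 0.25 | 8% | 12% | 17% |
| 0.5 | 17% | 35% | 52% |
| 0.75 | 32% | 66% | 85% |
| 1.0 | 51% | 88% | 98% |

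If each yearly check looked only at that year's 6 schools, the 6-school column would apply every time.

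**Step 4: two metrics.** The rule acts if either metric is off. With the same d on both and independence, the chance is 1 − (1 − p)². At 6 schools, d = 0.5, 0.75 and 1.0 give 31%, 54% and 76%.

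**Step 5: with the rural frame as benchmark.** Then d = 0 for a random rural sample, whatever the rural-state gap. Under the same illustrative test the flag rate is 5% per metric, or 1 − 0.95² = 9.8% on either.

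**The case against.** The strongest reply has four parts.

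- **The harm is conditional.** It needs rural schools to differ from the state, and the documents do not show that they do. The Background lists lower socioeconomic status among barriers for rural children, but gives no figure and does not speak of schools. This stands. At d = 0.25 the flag rate is only 8% with 6 schools and 12% with 12.
- **The test is imported.** Section II.E says Adoption is descriptive, and no section sets a level or threshold. This stands, and the percentages above are illustration only. It does not remove the yearly decision in II.A, which must rest on some judgement against some reference.
- **The link to oversampling is inferred.** This stands. The Adoption wording might even be shorthand for the rural list in II.A; the documents cannot settle that. On either reading the text needs to name the reference.
- **The randomised comparison is untouched.** This stands. Both arms come from the same recruited schools, which are stratified on these two variables before assignment.

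A reader might also infer that the rule steers recruitment away from the target population. The documents do not support that: only rural schools are approached and families must be rural, so oversampling can change only the mix within rural schools.

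**Conclusion.** The mismatch between sampling frame and Adoption benchmark is certain from the text. Its consequence is conditional. If rural schools differ from the state on school size or percent free/reduced lunch, a sample that represents rural Kansas well can be described as unrepresentative. If the yearly oversampling uses the same benchmark, later cohorts would tilt toward rural schools that look like the state average.

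Under the assumed test, the effect on recruitment decisions is small at a 0.25 SD difference and material from about 0.5 SD (17% with 6 schools, 35% with 12). The 18-school figures concern the final description only. It would be tempting to conclude that a correct rural sample will be called unrepresentative, but the documents supply neither the rural-state difference nor the criterion needed for that. The effect is confined to the Adoption outcome, the recruitment mix and generalisability. The point is worth correcting because the stated comparator is the wrong one for a rural trial and the correction is cheap.

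**What to change.** - In section II.D, item 2, make the 550 rural elementary schools in the sampling frame the benchmark for Adoption.
- In section II.A, state that the yearly oversampling decision uses that same benchmark for the remaining cohorts.
- Keep the all-Kansas comparison, if wanted, as background description.

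The cost is two short text edits and restricting the statewide school data to the rural schools already on the mailing list. No new participants or measurements are needed. There is one small downside: if some cohorts have already been recruited, the report must say which benchmark guided the earlier yearly decisions. Changing the benchmark does not by itself define when schools count as not representative; a sentence giving that criterion would sensibly go in with the same edit.
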